10.0 Adverse Events: List And Reporting Requirements

10.1 Adverse Events and Potential Risks List

Expected toxicities include fatigue and skin reactions within the radiation field. Erythema, dry and moist desquamation of the skin will be recorded weekly as described in Appendix 1. Breast edema and tenderness are additional possible acute side effects. Acute and late toxicity will be reported as scheduled in the study calendar.

Adverse events (AEs) will be recorded in the case report form for the duration of the trial, regardless of whether or not the event(s) are considered related to the trial. All AEs considered related to trial medication will be followed until resolution even if this occurs post-trial.

Definitions of adverse events

Adverse event (AE)

Any untoward medical occurrence in a clinical investigation patient administered a treatment that does not necessarily have a causal relationship with this treatment. An adverse event (AE) can, therefore, be any unfavorable and unintended sign (including an abnormal finding), symptom, or disease temporally associated with the use of an investigational procedure, whether or not related to the investigational procedure.

Serious adverse event (SAE)

An adverse event occurring at any dose that results in any of the following outcomes:

- death
- a life-threatening adverse experience
- inpatient hospitalization or prolongation of existing hospitalization excluding those for administration, transfusional support, disease staging/re-staging procedures, thoracentesis/paracentesis, or placement of an indwelling catheter, unless associated with other serious events.
- persistent or significant disability/incapacity, or
- congenital anomaly/birth defect.

Important medical events that may not result in death, be life-threatening, or require hospitalization may be considered serious adverse drug experiences when, based upon appropriate medical judgment, they may jeopardize the patient or subject and may require medical or surgical intervention to prevent one of the outcomes listed above.

Death, regardless of cause, which occurs within 30 days of the last dose of or after 30 days and is a result of delayed toxicity due to administration of the , should be reported as a serious adverse event.

Unexpected adverse event

An adverse event that is not mentioned in the informed consent or the specificity or severity of which is not consistent with the study's informed consent.

Life-threatening

Any adverse drug experience that places the patient or subject, in the view of the investigator, at immediate risk of death from the reaction as it occurred. It does not include a reaction that, had it occurred in a more severe form, might have caused death.

Reporting adverse events

Adverse events

Adverse events will be recorded for the duration of a patient's participation in the trial. All adverse

events (except grade 1 and 2 laboratory abnormalities unless a dose treatment modification, delay or therapeutic intervention is required), regardless of causal relationship, are to be recorded in the case report form and source documentation. Pre-existing conditions at baseline will be recorded. If a pre-existing condition does not change, it does not have to be reported on subsequent cycles. The investigator must determine the toxicity of adverse events according to the CTC version 4.0 (Appendix 1) and their causal relationship.

Serious adverse events

Adverse events classified as serious require expeditious handling and reporting to comply with regulatory requirements.

All serious adverse events, whether considered to be related or not, require that a Serious Adverse Event Report Form be completed within 24 hours of the investigator becoming aware of the event. The investigator must immediately report all unexpected serious adverse events to the Institutional Review Board in writing.

Serious adverse events will be reported to:

Name [name].
[name],
[name]
[contact]
[contact]

10.2 Medical Monitor

This study will be monitored by the WCMC Data Safety Monitoring Committee according to the procedures of the WCMC Data Safety Monitoring Plan. The WCMC DSMB committee will be the medical monitor of the study.

10.3 DSMB safety Review

The protocol will be reviewed by the Data Safety Monitoring Board (DSMB) on a Semi-annual basis. Safety reports will be submitted to the DSMB every six months.

10.4 Expedited Adverse Event Reporting

All serious adverse events, whether considered to be drug-related or not, require that a Serious Adverse Event Report Form be completed within 24 hours of the investigator becoming aware of the event. The investigator must immediately report all unexpected serious adverse events to the Institutional Review Board in writing. Expedited AE reporting will utilize the descriptions and grading scales as presented in Appendix 1. The rest of the events (SAE or any other) will be brought to attention of the Data Safety Monitoring Committee. The IRB would need to see their regular reports as a result of analysis of all SAEs and AEs.

11.0 Correlative/Special Studies

11.1 Blood collection for TGF-beta 1 polymorphism determination

Approximately 30 cc of blood will be obtained by venipuncture once before starting treatment and once on the last day of treatment, after the last dose of radiation. The specimens will be aliquoted to store part of them for future testing of other polymorphisms and other related research studies.

12.0 Storage Of Samples

All blood samples will be processed immediately and stored indefinitely for later analysis in a locked -80°C freezer in WCMC for research purposes only. These specimens will not be linked to any clinical data and will be de-identified in the clinical research database, only the Principal investigator and the data manager will have access to the master list with the patient name and an identification number. This master list will be secured in a locked cabinet at the WCMC. Only the investigators listed on this protocol will have access to these samples. After blood samples are analyzed at a later date, any unutilized samples will be preserved indefinitely in WCMC for potential future research.

All patients enrolled will be given a unique identifier (study ID number). Only the data manager will know the code linking patient and study ID number. Patients will be assigned a unique code number. All specimens collected will be de-identified and assigned the same unique study number of the corresponding patient and will also be marked with the collection time point. Clinical information regarding toxicities and response will likewise be stored in a de-identified database using only the unique identifier (study ID number).

All blood samples will be stored indefinitely until appropriate funding has been obtained to perform correlative studies or until subject withdraws consent for banking of study specimens. If consent is withdrawn by the study subject, samples will be destroyed as per standard practices.

The storage of blood is optional and subject may withdraw consent for the banking of these specimens at any time. The subject may make this request by writing to the Principal Investigator [name]. at New York –Presbyterian Weill Cornell Medical Center, [name].

12.1 Research Conflict Of Interest

There are no conflicts of interest to report.

12.3 Cost To Subjects

Each subject or their insurance company will be charged and held responsible for the costs of care provided as part of this study. Radiotherapy is a standard treatment for breast cancer and will be billed to subjects and their insurance companies.

There will be no monetary compensation for participating in this study.

12.4 Optional Genetic Research

Part of the blood samples will be stored for DNA/RNA related studies. As with all research samples obtained in this study, patient samples will be de-identified and coded with a unique # that allows only the researchers of this study to gather information about patients if necessary.

The Principal Investigator and the data manager will know the code linking patients and study ID number through a master list; this master list will be kept in a secured, locked cabinet at the WCMC. No one outside of this study will have access to the patients' samples.

Patients will not be notified of the results of the future research. The results of the future research might be used in presentations and publications without any identifiers that might link results directly to patients.

Patients may choose to withdraw their permission to use the samples in the future research, and may do so at any time by writing to the Principal Investigator [name]. at New York –Presbyterian Weill Cornell Medical Center, Department of Radiation Oncology, [name].

12.5 Coding of Samples

Specimens will be given a Study ID number and will be otherwise de-identified for privacy protection. The study data manager will keep the list of samples.

13.0 Study Calendar

Study	Pre Treatment	Weekly	Last week	Post Treatment (day 45-60)	Post Treatment (once/year)
History & Physical	X				
Toxicity evaluation	X	X		X	X
CBC with differential	X	X			
Comprehensive metabolic	X	as clinically indicated			
Mammogram and/or breast MRI ^a	X				X
Lumpectomy pathology report	X				
BREAST-focused exam, KPS	X	X		X	X
Blood for TGF-BETA polymorphisms	X		X ^b		
Quality of Life Questionnaires ^c	X		X	X	X
LENT/SOMA assessment					X ^c

- a. Standard mammogram or MRI for both breasts.
- b. Last day of treatment, after last dose of radiation
- c. QOL will be assessed using the Breast Cancer Treatment Outcome Scale (BCTOS) [30] MOS SF- 36 Vitality Scale (see appendix 4) at baseline, last week of radiation treatment, 45-60 days from starting radiotherapy and 2 year follow-up.
- d. Patients will be seen after completion of treatment (at day 45-60) and then yearly for five years to assess long term sequelae by LENT/SOMA scale.

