8.0 Surgery

Patients will have completed all surgical procedures related to breast cancer surgery prior to accrual into this protocol in order to establish eligibility criteria. Final pathology margins must be at least 1 mm in all directions to be eligible. The patient may undergo re-excision if the initial margins are involved or close (< 1mm). If the patient meets the eligibility criteria after re-excision, she may be entered onto the study. Patients undergoing reconstructive surgery are eligible either after maximum expansion of tissue expanders or after completion of breast reconstruction.

While currently women with a variety of clinical presentations of breast cancer are offered a neo-adjuvant systemic approach (stage I-III), eligibility to this protocol will require assessment of nodal status at surgery, either by sentinel node and/or axillary dissection (minimum 6 nodes).

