16.1.2 Secondary endpoints

Acute toxicities, Quality of Life of patients before during and after treatment
Late toxicity 60 days post treatment including brachial plexopathy, fibrosis and telangiectasia; the proportion of patients with grades 2 or higher toxicity

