16.6.2 Secondary Endpoints

See primary endpoint.

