Appendix 1. – Common Toxicity Criteria

Acute Toxicity from *Common Terminology Criteria for Adverse Events v4.0 (CTCAE)*, Published: May 28, 2009

	Grade 0	Grade 1	Grade 2	Grade 3	Grade 4
FATIGUE	No change	Mild fatigue over baseline	Moderate or causing difficulty performing some ADL	Severe fatigue interfering with ADL	Disabling
RADIATION DERMATITIS	No change	Faint erythema or dry desquamation	Moderate to brisk erythema; patchy moist desquamation, mostly confined to skin folds and creases; moderate edema	Moist desquamation other than skin folds and creases; bleeding induced by minor trauma or abrasion	Skin necrosis or ulceration of full thickness dermis; spontaneous bleeding from involved site
PAIN	No pain	Mild pain not interfering with function	Moderate pain; pain or analgesics interfering with function, but not interfering with ADL	Severe pain; pain or analgesics severely interfering with ADL	Disabling

Table 1. RTOG/EORTC and LENT/SOMA classification of late effects

RTOG/EORTC	Grade 1	Grade 2	Grade 3	Grade 4
Skin	Slight atrophy, pigmentation change, some hair loss	Patchy atrophy, moderate telangiectasia, total hair loss	Marked atrophy, gross telangiectasia	Ulceration
Subcutaneous tissue	Slight induration (fibrosis), and loss of subcutaneous fat	Moderate fibrosis, but asymptomatic; slight field contracture, $\leq 10\%$ linear reduction	Severe induration and loss of subcutaneous tissue, field contracture, $\geq 10\%$ linear reduction	Necrosis
LENT/SOMA				
Breast				
Subjective				
Pain	Occasional and minimal Hypersensation, pruritus	Intermittent and tolerable	Persistent and intense	Refractory and excruciating
Objective				
Telangiectasia	$<1\text{ cm}^2$	$1\text{--}4\text{ cm}^2$	$>4\text{ cm}^2$	
Fibrosis	Barely palpable, increased density	Definite increased intensity and firmness	Very marked density, retraction, and fixation	
Edema	Asymptomatic	Symptomatic	Secondary dysfunction	
Retraction, atrophy	10–25%	$>25\text{--}40\%$	$>40\text{--}75\%$	Whole breast
Ulcer	Epidermal only, $<1\text{ cm}^2$	Dermal only, $>1\text{ cm}^2$	Subcutaneous	Bone exposed, necrosis
Lymphedema, arm circumference	2–4-cm increase	$>4\text{--}6\text{-cm}$ increase	$>6\text{-cm}$ increase	Useless arm
Skin				
Pigmentation change	Transitory, slight	Permanent, marked	—	—

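### No LENT/SOMA score is scheduled before radiation, so fibrosis already present after surgery can be counted as late radiation toxicity

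*Combined protocol and SAP*

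**What the plan says.** - **Timing of the score.** In section 13.0 the "LENT/SOMA assessment" row has one mark, under the yearly post-treatment column. The pre-treatment cell is blank. Footnote d says that patients will be "seen after completion of treatment (at day 45-60) and then yearly for five years to assess long term sequelae by LENT/SOMA scale".
- **Endpoint.** Section 16.1.2 names "Late toxicity 60 days post treatment including brachial plexopathy, fibrosis and telangiectasia" and measures it as "the proportion of patients with grades 2 or higher toxicity".
- **Analysis.** Section 16.6.2 reads, in full, "See primary endpoint". Section 16.6.1 then supplies a proportion with an exact 95% confidence interval.
- **Population.** Section 8.0: "Patients will have completed all surgical procedures related to breast cancer surgery prior to accrual into this protocol". The same section admits patients with expanded tissue expanders or a completed reconstruction.
- **Scale.** The grade 2 anchor for fibrosis on LENT/SOMA (Appendix 1) is "Definite increased intensity and firmness".
- **Baseline information that is collected.** The calendar marks a breast-focused exam and a toxicity evaluation before treatment. Section 10.1 has pre-existing conditions recorded under adverse-event reporting. The baseline questionnaire (Appendix 3.1) asks the patient about hardening, scar tissue and skin thickening.

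**The concern.** Section 1.2 sets out to assess how often late radiation toxicity occurs. That requires knowing who was free of the condition when radiation began. The grade 2 fibrosis anchor is a finding on palpation that says nothing about cause, and an operated or reconstructed breast may already meet it. The study is non-randomized and its two cohorts are analysed separately (sections 6.3 and 16.3), so no control group can show how much of the firmness seen later was left by surgery. What is at stake is the interpretation of a stated secondary endpoint: a rate presented as the late toxicity of this regimen could include change that the regimen did not cause.

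**Working it through.** The plan gives no design figure for late toxicity, so there is nothing to reproduce. The check has two parts.

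**1. Is there any route by which pre-existing fibrosis would be separated out?**

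- *Calendar.* Whether footnote d is read as yearly visits only or as day 45-60 plus yearly visits, every LENT/SOMA score falls after radiation.
- *Endpoint and analysis.* Neither 16.1.2 nor 16.6.2 mentions change from baseline, worsening or attribution.
- *Pre-treatment toxicity evaluation.* The Appendix 2 form covers fatigue, dermatitis and breast pain. It has no fibrosis item and no pre-treatment box.
- *Breast-focused exam.* Its content is not defined.
- *Pre-existing conditions (section 10.1).* This is an adverse-event reporting rule with no link to the LENT/SOMA endpoint.
- *Baseline questionnaire.* It is patient-reported and uses different scales from the clinician's LENT/SOMA grade.

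Some cases could be recognised from these sources, but no text says that they will be used to correct the proportion.

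**2. How large could the effect be?**

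Inputs:

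- r, the proportion in whom radiation causes grade 2 or higher fibrosis: assumed 10%. This is the middle of the 5-15% that section 4.2 gives as commonly reported, although that range is not tied there to a LENT/SOMA grade.
- b, the proportion with grade 2 or higher before radiation that persists to scoring: not in the documents, assumed 0% to 15%.
- n = 37 per cohort (section 16.3).

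Formula: reported rate = b + (1 - b) × r. It assumes that pre-existing change persists and that radiation affects the remaining patients at rate r.

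| b (assumed) | Calculation | Reported rate | Expected cases in 37 |
|---|---|---|---|
| 0% | 0 + 1.00 × 0.10 | 10.0% | 3.7 |
| 5% | 0.05 + 0.95 × 0.10 | 14.5% | 5.4 |
| 10% | 0.10 + 0.90 × 0.10 | 19.0% | 7.0 |
| 15% | 0.15 + 0.85 × 0.10 | 23.5% | 8.7 |

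Sensitivity to r at b = 10%: r = 5% gives 0.10 + 0.90 × 0.05 = 14.5%, and r = 15% gives 0.10 + 0.90 × 0.15 = 23.5%. The share of counted cases that pre-date radiation is b divided by the reported rate: 0.10/0.145 = 69% at r = 5%, 0.10/0.19 = 53% at r = 10%, and 0.10/0.235 = 43% at r = 15%.

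**The case against.** The strongest reply is that baseline information does exist. There is a pre-treatment exam, pre-existing conditions are recorded, the investigator must judge causality for adverse events, and the questionnaire items on hardening are repeated at follow-up. A reader might infer that surgical fibrosis *will* be counted as radiation toxicity. The documents do not establish that, only that it *can* be, because nothing in the endpoint definition prevents it.

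Other stronger readings also fail:

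- *That LENT/SOMA is certainly confined to yearly visits.* Footnote d can be read as including day 45-60.
- *That arm swelling, edema and retraction contaminate the endpoint.* They are separate rows in Appendix 1 and are not named in section 16.1.2. The documents also give no reason to expect surgery to produce telangiectasia. The concern is mainly fibrosis.
- *That the arm-circumference item cannot be scored without a baseline.* Appendix 1 names no comparator, and the untreated side is a possible one.
- *That the genetic analysis is biased in the same way.* Section 4.4 uses grade 3 and 4 complications at 3 years, so pre-existing change would have to be that severe and last that long.

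It is also fair to say that this is a secondary endpoint with no decision rule, that the bias would overstate toxicity rather than hide it, and that precision is limited anyway: 4 cases in 37 gives an exact 95% interval of 3.0% to 25.4%. All of this limits the consequences. None of it supplies a baseline, and a confidence interval does not cover this kind of error.

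**Conclusion.** The point holds in limited form. No LENT/SOMA score precedes radiation, the endpoint is an unadjusted proportion, and all patients have had surgery, so pre-existing fibrosis can enter the late-toxicity rate. The documents cannot settle the size. With r assumed at 10%, the overstatement is nil at b = 0 and 13.5 percentage points (23.5% less 10.0%) at b = 15%, provided the pre-existing change persists. The primary dermatitis endpoint and any conclusion drawn from it are untouched, and the genetic analysis is reached only through persisting grade 3-4 change. It is worth correcting because the unknown quantity is easy to measure before radiation and cannot be reliably recovered afterwards. Section 4.2 itself describes visual assessment and palpation as subjective, which makes later grading from unstructured notes weak.

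**What to change.** 1. In section 13.0, add a pre-treatment mark to the LENT/SOMA row, scored at the breast-focused exam already scheduled there.
2. In section 16.1.2, define late toxicity as grade 2 or higher and worse than the pre-treatment grade, and report the raw proportion alongside it. The raw figure is still needed, because a patient already at the top fibrosis grade cannot worsen on the scale.
3. In section 16.6.2, state this analysis explicitly.
4. Reconcile the LENT/SOMA row with footnote d, so that it is clear whether day 45-60 is a scoring visit. The row appears to carry the quality-of-life footnote letter instead of d.

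**Cost.** A few minutes per patient at an existing visit. Patients already treated have no baseline score. For them, a sensitivity analysis could compare the raw rate with a rate that excludes those whose baseline exam notes or questionnaire answers indicate existing hardening, reported as approximate.

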14.0 Measurement Of Effect

14.1 Response Review

Since the first main endpoint of this study is to compare the toxicity profile of the regimen, the study nurse will assess the acute toxicity for radiation by recording the findings on the form attached in Appendix 3.

15.0 Data Reporting / Regulatory Considerations

The WCMC Data and Safety Monitoring Committee (DSMC) is the central monitoring board for this study. The WCMC Cancer Institute Data and Safety Monitoring Committee (DSMC) is the local monitoring board for WCMC patients.

15.1 Monitoring plan

This study will be conducted in accordance with the guidelines in the 2001 NCI approved data Safety and Monitoring plan for the WCMC Cancer Institute and with the WCMC approved data Safety and Monitoring plan for the WCMC Cancer Institute. Monitoring will occur on a yearly basis from the date the first patient is enrolled. Reports to the Data Safety and Monitoring Committee will include the following information: accruals, targets, responses, adverse events and evidence of reporting to appropriate review committees. The WCMC Data and Safety Monitoring Board (DSMB) will review the IRB approved protocol, the data and safety monitoring plan and any stopping guidelines during protocol initiation. During the course of the study, the DSMB will review cumulative study data twice a year to evaluate safety, efficacy, study conduct, and scientific validity and integrity of the trial. The WCMC DSMB may also convene as needed if stopping criteria are met or other safety issues arise that the Principal Investigator and/or IRB would like the WCMC DSMB to address.

15.2 Stopping rules

Treatment will be held if patients experience > Grade 2 radiation dermatitis. Patients will be monitored until the resolution of the adverse event. Based on PI's discretion, patients will resume or be withdrawn from the study. Adverse Events will be recorded based on CTCAE v4.03.

If safety concerns arise, the DSMC will identify these concerns and recommend modification or termination of the clinical trial. There is no formal interim analysis for this trial.

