16.3 Accrual estimates

Two distinct cohorts will be tested in this study. Based on the algorithm presented in study design (Page 9) some patients will need post-operative radiation to the breast/chest wall alone

(cohort 1) or to the breast and level III /SCV nodes (cohort 2). Since the fields of accelerated radiation are different the 2 cohorts will be accrued separately and analyzed separately.

Estimated number of eligible patients for the trial is 2-4/month. Therefore, we estimate that the required 74 patients (37 per cohort) will be recruited within 24-36 months.

With 37 patients, we can detect a difference of 18% from a baseline rate of 25% (grade II-III acute dermatitis) with a 2-sided $\alpha = 0.05$ and power of 80% using an exact binomial test. If we observe 15 or more events among these 37 patients, the null hypothesis that the rate is 25% will be rejected. Calculations from PASS 2008, NCSS.

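### Section 15.1 relies on stopping criteria that are never defined, so nothing triggers a pause or DSMB contact when a cohort's 15th event settles the section 16.3 test

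*Combined protocol and SAP*

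**What the plan says.** - **Section 15.1 (Monitoring plan):** the DSMB reviews any stopping guidelines at protocol initiation and cumulative data twice a year. It "may also convene as needed if stopping criteria are met", or if other safety issues arise. The criteria are not given there.
- **Section 15.2 (Stopping rules):** the only explicit trigger is a hold on an individual patient's treatment. At trial level the DSMC may recommend modification or termination if it has safety concerns, with no count or rate attached. The section ends: "There is no formal interim analysis for this trial".
- **Section 16.5:** no interim analyses are planned.
- **Section 10.3:** safety reports go to the DSMB every six months.
- **Section 16.3:** "If we observe 15 or more events among these 37 patients, the null hypothesis that the rate is 25% will be rejected". Also, "the 2 cohorts will be accrued separately and analyzed separately", so the count applies to each cohort on its own.

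**The concern.** A reader of 15.1 would expect to find, somewhere, the criterion that brings the DSMB together between scheduled reviews. There is none. The omission matters because 16.3 already contains a natural one. Events only accumulate, so once a cohort has 15 of them, no outcome among its remaining patients up to number 37 can reverse the rejection of 25%. At that moment the trial's own rule has gone against the target in the Protocol Summary (grade 2–3 dermatitis below 25% in each cohort). Even so, neither the study team nor the DSMB is told that this count calls for a decision. New patients could go on entering that cohort until the next scheduled review without anyone having decided that they should.

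**Working it through.** **Inputs.** From 16.3: 37 patients per cohort, null rate 25%, detectable difference 18 points (so 43%), rejection at 15 or more events, accrual 2–4 per month over both cohorts. From the Protocol Summary: about 3 per month overall. From 7.2 and 16.6.1: up to 21 days of treatment, then a 60-day endpoint window.

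**1. The plan's own figures.** With X ~ Binomial(37, 0.25), the two-sided exact p-value is 0.086 at 14 events and 0.036 at 15, so the critical count of 15 reproduces. The upper-tail error is P(X ≥ 15 | 0.25) = 0.027. The stated power does not reproduce: P(X ≥ 15 | 0.43) = 0.678, against the plan's "power of 80% using an exact binomial test". That is a separate matter. The figures below use the 15-event rule as written.

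**2. Stopping at the 15th event leaves the test unchanged.** Let T be the number of the patient who has the 15th event:

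P(T = t) = C(t−1, 14) · p^15 · (1−p)^(t−15), for t = 15, 16, …

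T ≤ 37 and X ≥ 15 are the same event. The rejection probability is therefore 0.027 at 25% and 0.678 at 43%, with or without the pause.

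**3. Patients not enrolled if accrual to the cohort ends there.** With outcomes known at once, the expected saving is Σ (37 − t) · P(T = t) over t = 15 to 37. If L further patients enter before the 15th event is known, it is Σ max(0, 37 − t − L) · P(T = t).

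For L: 21 + 60 = 81 days is about 2.66 months. At 1–2 patients per month per cohort (2–4 overall, assumed even split), that is 2.7 to 5.3, or about 3 to 5 patients.

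| True rate | P(15th event by patient 37) | P(15th event before patient 37) | Saving, no lag | Saving, L = 5 to 3 |
|---|---|---|---|---|
| 25% | 0.027 | 0.02 | 0.1 | under 0.1 |
| 43% | 0.678 | 0.63 | 4.0 | 1.4–2.2 |
| 50% | 0.906 | 0.88 | 7.4 | 3.4–4.8 |
| 60% | 0.995 | 0.99 | 12.0 | 7.1–9.1 |

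At 43%, the chance of saving any patient falls from 0.63 with no lag to 0.33–0.45 with L = 5 to 3.

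**4. Entries between six-monthly reviews.** 3 per month × 6 months ÷ 2 cohorts = 9 per cohort. At 2 and 4 per month the figures are 6 and 12. The even split is an assumption.

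**5. Effect on the estimate.** If a cohort stops at T, the naive proportion is 15/T; otherwise it is X/37. Its expectation exceeds the true rate by 1.1 points at 43% and 1.6 points at 60%.

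**The case against.** Having no formal interim analysis is a declared choice, and oversight exists: twice-yearly review, ad hoc meetings, and DSMC power to recommend termination. Several stronger readings are tempting, and the documents do not support them.

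- **That the plan obliges a cohort to continue to 37.** It does not. Continued enrolment is possible, not prescribed, because the committee can act at its discretion.
- **That 15 events show the regimen to exceed 25%.** The 16.3 test rejects, but the equal-tailed exact 95% interval for 15/37 is 24.8% to 57.9%, which contains 25%. Section 16.6.1 plans exact intervals without naming the type.
- **That later patients add nothing.** They cannot change the test, but they add precision to the 16.6.1 proportion and to the late-toxicity estimates.
- **That the result is certain whatever the final size.** It is certain only at n = 37. The Protocol Summary allows an accrual ceiling of 100 and 16.2 analyses all registered patients. At n = 38, 15 events gives a two-sided p of 0.058.
- **That 18 patients could enter the cohort between reviews.** That is the whole-trial figure at 3 per month.

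It is also fair to say that the count mixes grades. Grade 2 in Appendix 1 includes moderate to brisk erythema, while section 16.0 defines feasibility by grade 3 events below 10%. That favours having the DSMB decide on continuation over closing the cohort automatically. The no-lag savings are ceilings, though weekly scoring during treatment should bring many events to light before the full 81 days.

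None of this supplies the criterion that 15.1 refers to.

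**Conclusion.** The point holds as a gap in the monitoring plan. Section 15.1 refers to criteria that do not exist at cohort or trial level, and the one count that settles the primary test triggers nothing. The cost of the gap depends on the true rate. It is negligible at 25%, on average 1.4 to 4.0 patients at the design alternative of 43%, and 7.1 to 12.0 at 60%. In each range the low end assumes 5 patients enter during the lag and the high end assumes no lag. The figures rest on the 15-of-37 rule as written, an analysis at exactly 37 patients, independent outcomes with a constant rate, an even split of accrual between cohorts, and accrual not resuming after the pause. The change is worth making because it is cheap and leaves the test's error (0.027 at 25%) and power (0.678 at 43%) as they are.

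**What to change.** In 15.2 and 16.5, state that primary-endpoint events are counted continuously in each cohort. When the count reaches the 16.3 critical number (15 as written, for n = 37), new accrual to that cohort is suspended and the DSMB is convened to decide on continuation. Make 15.1 refer to this criterion. If the critical count or the cohort size in 16.3 is revised, or a cohort may exceed 37, the trigger must be restated to match.

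The cost is protocol wording and a running tally. A stopped cohort gives fewer patients for the 16.6.1 proportion and for late toxicity, and the naive proportion is biased slightly upward. Section 16.6.1 should say that this will be noted when the result is reported. Care of patients already on treatment is outside this point.
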